**Table 7. Specific Toxicity Management Guidelines for Abnormal Laboratory Values**

Laboratory Parameter	Toxicity Management Guideline
Hemoglobin	
 
• If hemoglobin < 8 g/dL interrupt study drug dosing and confirm by repeat testing with a new sample.
 
• If hemoglobin decreases <math>\geq 3.0</math> g/dL from baseline without an alternative etiology, interrupt study drug dosing and confirm by repeat testing with new sample.
 
• If hemoglobin decreases <math>\geq 3.0</math> g/dL from baseline and an alternative etiology is known, the subject may remain on study drug at the investigator's discretion.
 
• If confirmed, continue to withhold study drug until hemoglobin value returns to normal reference range or its baseline value.
 

Absolute neutrophil count (ANC)	
 
• If confirmed < 1000/<math>\mu</math>L by repeat testing with new sample, interrupt study drug dosing until ANC value returns to normal reference range or its baseline value.
 
• Discontinue study drug if confirmed < 500/<math>\mu</math>L by repeat testing with new sample.
 

Absolute lymphocyte counts (ALC)	
 
• If confirmed < 500/<math>\mu</math>L by repeat testing with new sample, interrupt study drug dosing until ALC returns to normal reference range or its baseline value.
 

Total white blood cell count	
 
• If confirmed < 2000/<math>\mu</math>L by repeat testing with new sample, interrupt study drug dosing until white blood cell count returns to normal reference range or its baseline value.
 

Platelet count	
 
• If confirmed < 50,000/<math>\mu</math>L by repeat testing with new sample, interrupt study drug dosing until platelet count returns to normal reference range or its baseline value.
 

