  - Total white blood cell count (WBC)  $< 2,500/\mu\text{L}$ ;
  - Absolute neutrophil count (ANC)  $< 1,500/\mu\text{L}$ ;
  - Platelet count  $< 100,000/\mu\text{L}$ ;
  - Absolute lymphocyte count  $< 800/\mu\text{L}$ ;
  - Hemoglobin  $< 10$  g/dL.
22. History of any of the following cardiovascular conditions:
  - moderate to severe congestive heart failure (New York Heart Association class III or IV);
  - Recent (within past 6 months) cerebrovascular accident, myocardial infarction, coronary stenting;
  - Uncontrolled hypertension as defined by a confirmed systolic blood pressure  $> 160$  mmHg or diastolic blood pressure  $> 100$  mmHg;
  - Any other condition which, in the opinion of the Investigator, would put the subject at risk by participating in the protocol.

23. Clinically relevant or significant ECG abnormalities, including ECG with QT interval corrected for heart rate (QTc) using Fridericia's correction formula (QTcF) > 500 msec.

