**Malignancy:** Subjects who develop malignancy other than NMSC or carcinoma in-situ of the cervix must be discontinued from study drug. Information including histopathological results should be queried for the confirmation of the diagnosis.

**ECG Abnormality:** Subjects must be discontinued from study drug for an ECG change considered clinically significant and with reasonable possibility of relationship to study drug OR a confirmed absolute QTcF value > 500 msec.

**Management of Select Laboratory Abnormalities:** For any given laboratory abnormality, the Investigator should assess the subject, apply the standard of care for medical evaluation and treatment following any local guidelines. Specific toxicity management guidelines for abnormal laboratory values (confirmation by repeat testing is required) are described in [Table 7](#) and may require an appropriate supplemental eCRF be completed. All abnormal laboratory tests that are considered clinically significant by the Investigator will be followed to a satisfactory resolution. If a repeat test is required per [Table 7](#), the repeat testing must occur as soon as possible.

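### Table 7 gives two unranked instructions when haemoglobin is below 8 g/dL after a fall of at least 3.0 g/dL with a known cause, and read literally its restart condition can already be met when a fall within the normal range is confirmed

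*Protocol*

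**What the plan says.** The haemoglobin row of Table 7 (Protocol Section 6.1.7) has four bullets, taken here in order.

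1. For a value below "8 g/dL interrupt study drug dosing and confirm by repeat testing with a new sample". Cause is not mentioned.
2. For a fall of at least 3.0 g/dL "from baseline without an alternative etiology, interrupt study drug dosing and confirm by repeat testing with new sample". The value need not be below the normal range.
3. For a fall of at least 3.0 g/dL "from baseline and an alternative etiology is known, the subject may remain on study drug at the investigator's discretion". No lower limit on haemoglobin is given.
4. The restart condition: "If confirmed, continue to withhold study drug until hemoglobin value returns to normal reference range or its baseline value".

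The text that introduces the table says only this: "Specific toxicity management guidelines for abnormal laboratory values (confirmation by repeat testing is required) are described in" Table 7. Neither that text nor the table ranks the bullets. The entry limit in Section 5.2.2 excludes screening values that meet "Hemoglobin $< 10$ g/dL".

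**The concern.** Bullet 1 is defined by the absolute value and bullet 3 by the change from baseline and its cause. The two definitions can be true of the same subject at the same visit. One then requires interruption and the other permits continuation. Separately, bullet 2 is defined by change from baseline, but one limb of bullet 4 is defined by the reference range, so a single value can satisfy both the trigger and the restart condition.

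The stake is subject protection and consistency between sites. Anaemia is an adverse event of special interest (Protocol Section 6.1.1.3). In the toxicity criteria of Appendix O, a fall of at least 3.0 g/dL is Grade 4 by itself, so every subject in the overlap of bullets 1 and 3 has a Grade 4 change. Two sites could handle the same event differently and each point to a bullet in support.

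**Working it through.** No planned figure is involved, so the check treats the bullets as conditions and finds where they hold together. Let B be baseline haemoglobin and H the on-study value, in g/dL.

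**Bullets 1 and 3, cause known**

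- Bullet 1 applies if H < 8.
- Bullet 3 applies if B − H ≥ 3.0, that is H ≤ B − 3.0.
- Both apply if H < 8 and H ≤ B − 3.0.

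If B ≥ 11, any H < 8 gives B − H > 3.0, so every value below 8 meets both. With values reported to 0.1, the highest value below 8 is 7.9. Full overlap then starts at B = 7.9 + 3.0 = 10.9. Below that it is partial:

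| Baseline | Both bullets apply | Bullet 1 alone applies |
|---|---|---|
| 10.9 or more | every value below 8 | none |
| 10.5 | 7.5 or lower | 7.6 to 7.9 |
| 10.0 | 7.0 or lower | 7.1 to 7.9 |
| 9.5 | 6.5 or lower | 6.6 to 7.9 |

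The last line is included because the 10 g/dL limit applies to screening. Table 2 schedules a further haematology sample at Baseline, and Section 8.1.5.3 defines baseline as the last value on or before the first dose. A baseline below 10 is therefore possible.

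Example: B = 12.0, H = 7.5, known bleed. The fall is 12.0 − 7.5 = 4.5. Bullet 1 says interrupt; bullet 3 says the subject may stay on drug.

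**Bullets 2 and 4, no alternative cause**

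- Bullet 2 applies if H ≤ B − 3.0.
- Bullet 4 is met if H is within the normal range or H is back at B. After a fall only the first limb can be true.
- Both hold for the same value if LLN ≤ H ≤ B − 3.0, with H no higher than the upper limit. This requires B ≥ LLN + 3.0, where LLN is the lower limit of normal.

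The documents give no haemoglobin reference range. Under assumed ranges, the in-range baselines affected are:

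| Assumed range (g/dL) | LLN + 3.0 | Baselines affected |
|---|---|---|
| Women 11.5–16.0 | 14.5 | 14.5 to 16.0 |
| Women 12.0–15.5 | 15.0 | 15.0 to 15.5 |
| Men 13.0–17.0 | 16.0 | 16.0 to 17.0 |
| Men 13.5–17.5 | 16.5 | 16.5 to 17.5 |
| Narrow, 13.0–15.5 | 16.0 | none within range |

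Example with the range 13.5–17.5: a man goes from 16.8 to 13.7. The fall is 3.1, so bullet 2 applies. The value 13.7 is within range, so the first limb of bullet 4 is true of the same value.

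**Comparison within Table 7**

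The first serum creatinine bullet triggers above 1.5 times baseline and above the upper limit of normal. It restarts at or below both. No value can meet trigger and restart together. The AST/ALT row interrupts first and then says how an alternative etiology is handled. The haemoglobin row does not state how its bullets interact.

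**The case against.** Bullets 2 and 3 look like a matched pair. They share one trigger and differ only in whether a cause is known, so the natural reading is that bullet 3 is an exception to bullet 2 and leaves bullet 1 untouched. Bullet 1 is also mandatory and bullet 3 permissive, so a site that interrupts below 8 g/dL breaches neither. Both arguments stand as far as they go, and they make this a drafting gap, not an unworkable rule. But the restriction of bullet 3 to bullet 2 is not written, and a site that relies on bullet 3 to continue dosing is outside bullet 1.

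On restart, to return to a range implies having left it. A subject who never left it could be read as having to return to baseline. That is a fair reading, but it is unstated.

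Four stronger inferences are tempting, and the documents do not support them.

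- A reader might infer that every value below 8 g/dL with a known cause is in conflict. It is not: the fall must also be at least 3.0 g/dL.
- A reader might infer that an in-range interruption ends at once. Bullet 2 stops dosing at the first value, and drug is held until the repeat sample confirms the fall.
- A reader might infer that a subject below normal needs full recovery. Re-entering the normal range is enough: with an assumed LLN of 12.0, a subject who fell from 15.0 to 11.9 meets the condition at 12.0, a rise of 0.1.
- A reader might infer that subjects are unprotected. Section 6.1.7 requires the investigator to assess each abnormality under standard of care, Section 5.4.1 requires discontinuation for clinically significant results that rule out continuing, and an external committee reviews unblinded safety data (Section 5.5.5.2).

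**Conclusion.** The point holds within these limits. In the current Table 7, a subject with haemoglobin below 8 g/dL, a fall of at least 3.0 g/dL and a known alternative cause meets an instruction to interrupt and a permission to continue, with no stated precedence. The overlap is complete from a baseline of about 11 g/dL and partial below it. This part rests only on the table's own numbers.

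The restart point is secondary. It depends on the literal wording of bullet 4 and arises only when baseline is at least LLN + 3.0 g/dL. How many subjects that covers cannot be computed, because neither the reference range nor the baseline distribution is given. The documents also give no event counts for the first part. No power, alpha or sample-size figure changes. This is an inexpensive clarification of a safety rule.

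**What to change.** The sponsor's medical team should reconcile the four haemoglobin bullets in Table 7 and state two things:

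- how bullets 1 and 3 interact when both are met;
- how the restart condition applies when the value that triggered the interruption is within the normal range.

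Which rule is right is theirs to decide, and no threshold or clinical rule is proposed here. The cost is the wording of one table cell in a protocol amendment, with notice to sites.

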**Table 7. Specific Toxicity Management Guidelines for Abnormal Laboratory Values (Continued)**

Laboratory Parameter	Toxicity Management Guideline
AST or ALT	
 
• Interrupt study drug immediately if confirmed ALT or AST <math>> 3 \times</math> ULN by repeat testing with new sample and either a total bilirubin <math>> 2 \times</math> ULN or an international normalized ratio <math>> 1.5</math>.               
 
○ A separate blood sample for INR testing will be needed to measure INR at the time of repeat testing for ALT or AST. A repeat test of INR is not needed for determination if above toxicity management criteria are met.
 
 
 
• Interrupt study drug immediately if confirmed ALT or AST <math>> 3 \times</math> ULN by repeat testing with new sample along with appearance of fatigue, nausea, vomiting, right upper quadrant pain or tenderness, fever, rash, and/or eosinophilia (<math>> 5\%</math>).
 
• Interrupt study drug immediately if confirmed ALT or AST <math>> 5 \times</math> ULN by repeat testing with new sample for more than 2 weeks.
 
• Interrupt study drug immediately if confirmed ALT or AST <math>> 8 \times</math> ULN by repeat testing with new sample.
 
 
Subjects who meet any of the above criteria should be evaluated for an alternative etiology of the ALT or AST elevation and managed as medically appropriate. The investigator should contact the AbbVie TA MD to discuss the management of a subject when an alternative etiology has been determined. The alternative etiology should be documented appropriately in the eCRF; study drug should be discontinued if no alternative etiology can be found.
 
For any confirmed ALT or AST elevations <math>> 3</math> ULN, complete supplemental hepatic eCRF.
 
 
• Subjects with HBc Ab+ (irrespective of HBs Ab status) and negative HBV DNA at screening who develop the following should have HBV DNA by PCR testing performed within 1 week:               
 
○ ALT <math>> 5 \times</math> ULN OR
 
○ ALT or AST <math>> 3 \times</math> ULN and either a total bilirubin <math>> 2 \times</math> ULN or INR <math>> 1.5</math> OR
 
○ ALT or AST <math>> 3 \times</math> ULN along with clinical signs of possible hepatitis
 
 
 
 
A positive result for HBV DNA PCR testing in these subjects will require immediate interruption of study drug and a hepatologist consultation should occur within 1 week for recommendation regarding subsequent treatment.

Serum Creatinine	
 
• If serum creatinine is <math>> 1.5 \times</math> the baseline value and <math>> \text{ULN}</math>, repeat the test for serum creatinine (with subject in an euvoletic state) to confirm the results. If the results of the repeat testing still meet this criterion then interrupt study drug and re-start study drug once serum creatinine returns to <math>\leq 1.5 \times</math> baseline value and <math>\leq \text{ULN}</math>.
 
• If confirmed serum creatinine <math>\geq 2</math> mg/dL, interrupt study drug and re-start study drug once serum creatinine returns to normal reference range or its baseline value.
 
 
For the above serum creatinine elevation scenarios, complete supplemental renal eCRF.

Creatine Phosphokinase	
 
• If confirmed CPK <math>\geq 4 \times</math> ULN and there are no symptoms suggestive of myositis or rhabdomyolysis, the subjects may continue study drug at the investigator's discretion.
 
• If CPK <math>\geq 4 \times</math> ULN accompanied by symptoms suggestive of myositis or rhabdomyolysis, interrupt study drug and contact AbbVie TA MD
 
 
For the above CPK elevation scenarios, complete supplemental CPK eCRF.

For allowed study drug interruption, the following rules apply:

### **Period 1**

- Upadacitinib/Placebo (daily dosing):
  - Allow study drug interruption  $\leq 14$  consecutive days for AEs and surgery during the first 26 weeks;
  - After Week 26, study drug interruption due to AEs/surgery is allowed  $\leq 21$  days.
- Adalimumab/Placebo (biweekly dosing):
  - Allow study drug interruption  $\leq 2$  consecutive missed doses for AEs and surgery during the first 26 weeks;
  - After Week 26, study drug interruption due to AEs/surgery is allowed  $\leq 3$  consecutive doses.
- If the subject must undergo emergency surgery, study drug should be interrupted at the time of the surgery.
- Elective surgery during the first 26 weeks is discouraged and needs to be discussed with the AbbVie Therapeutic Area Medical Director.
- If the subject undergoes elective surgery, the subcutaneous study drug should be interrupted two weeks prior to the planned surgery and the oral study drug should be interrupted 1 week prior to the planned surgery.
- After surgery, allow reintroduction of study drug once the physician has examined the surgical site and determined that it has healed and there is no sign of infection.

### **Period 2**

- Upadacitinib/Placebo (daily dosing):
  - Up to 30 consecutive days of oral study drug interruption is allowed.
- Adalimumab/Placebo (biweekly dosing):
  - Study drug interruption due to AEs/surgery is allowed  $\leq 3$  consecutive doses.

- If the subject undergoes elective surgery, the subcutaneous study drug should be interrupted 2 weeks prior to the planned surgery and the oral study drug should be interrupted 1 week prior to the planned surgery.
- If the subject must undergo emergency surgery, the study drug should be interrupted at the time of surgery.
- After surgery, allow reintroduction of study drug once the physician has examined the surgical site and determined that it has healed and there is no sign of infection.

### **6.1.8 Data Monitoring Committee**

An external DMC will review unblinded safety data. See Section 5.5.5.2 for details.

### **6.1.9 Cardiovascular Adjudication Committee**

An independent committee of physician experts in cardiovascular adjudication will be utilized to assess potential cardiovascular AEs in a blinded manner as defined by the Cardiovascular Adjudication Committee charter.

## **6.2 Product Complaint**

### **6.2.1 Definition**

A Product Complaint is any Complaint (see Section 6.0 for the definition) related to the biologic or drug component of the product.

For a product this may include, but is not limited to, damaged/broken product or packaging, product appearance whose color/markings do not match the labeling, labeling discrepancies/inadequacies in the labeling/instructions (example: printing illegible), missing components/product, or packaging issues.

Any information available to help in the determination of causality to the events outlined directly above should be captured.

## **6.2.2 Reporting**

Product Complaints concerning the investigational product must be reported to the Sponsor within 1 business day of the study site's knowledge of the event via the Product Complaint form. Product Complaints occurring during the study will be followed-up to a satisfactory conclusion. All follow-up information is to be reported to the Sponsor (or an authorized representative) and documented in source as required by the Sponsor. Product Complaints associated with adverse events will be reported in the study summary. All other complaints will be monitored on an ongoing basis.

Product Complaints may require return of the product with the alleged complaint condition. In instances where a return is requested, every effort should be made by the Investigator to return the product within 30 days. If returns cannot be accommodated within 30 days, the site will need to provide justification and an estimated date of return.

The description of the complaint is important for AbbVie in order to enable AbbVie to investigate and determine if any corrective actions are required.

## **7.0 Protocol Deviations**

AbbVie does not allow intentional/prospective deviations from the protocol unless when necessary to eliminate an immediate hazard to study subjects. The Principal Investigator is responsible for complying with all protocol requirements, and applicable global and local laws regarding protocol deviations. If a protocol deviation occurs (or is identified) after a subject has been enrolled, the Principal Investigator is responsible for notifying IEC/IRB regulatory authorities (as applicable), and the following AbbVie Clinical Contacts:

Primary Contact:

Alternate Contact:

Such contact must be made as soon as possible to permit a review by AbbVie to determine the impact of the deviation on the subject and/or the study.

Examples of protocol deviations include the following:

- Subject entered into the study even though she/he did not satisfy entry criteria;
- Subject who developed withdrawal criteria during the study and was not withdrawn;
- Subject who received wrong treatment or incorrect dose;
- Subject who received excluded or prohibited concomitant treatment.

## **8.0 Statistical Methods and Determination of Sample Size**

### **8.1 Statistical and Analytical Plans**

Unless otherwise specified, statistical tests will be at two-sided significance level of 0.05 for efficacy analyses and all other analyses. A test will be deemed significant if the *P* value is less than or equal to 0.05 unless otherwise specified.

An unblinded analysis will be conducted after all subjects have completed Week 26 for the purpose of regulatory submission. To maintain integrity of the trial and avoid introduction of bias, study sites and subjects will remain blinded for the duration of

Period 1. Additional unblinded analyses may be conducted after the Week 26 unblinded analysis for regulatory purposes.

Completed and specific details of the statistical analysis will be described and fully documented in the Statistical Analysis Plan (SAP). The SAP will be finalized prior to the database lock for the Week 26 analysis. The statistical analyses will be performed using SAS (SAS Institute Inc., Cary, NC, USA).

### **8.1.1 Analysis Populations**

#### **8.1.1.1 Full Analysis Set (FAS)**

The Full Analysis Set (FAS) includes all randomized subjects who received at least one dose of study drug. The FAS will be used for all efficacy and baseline analyses.

#### **8.1.1.2 Per Protocol Analysis Set**

The Per Protocol Analysis Set represents a subset of the FAS and consists of all FAS subjects who did not meet any major protocol violations during the study. Definitions of major protocol violations will be detailed in the SAP. Additional analysis may be conducted on the Per Protocol analysis set, in order to evaluate the impact of major protocol violations.

#### **8.1.1.3 Safety Analysis Set**

The Safety Analysis Set consists of all subjects who received at least one dose of study drug. For the Safety Analysis Set, subjects are assigned to a treatment group based on the treatment actually received, regardless of the treatment randomized.

### **8.1.2 Subject Accountability, Disposition and Study Drug Exposure**

#### **8.1.2.1 Subject Accountability**

The following will be summarized by site and by treatment group as well as overall, separately for Period 1 and Period 2: number of subjects randomized, the number of

subjects who received at least one dose of study drug, the number of subjects who completed, the number of subjects who prematurely discontinued study drug, and the number of subjects who prematurely discontinued study participation.

#### **8.1.2.2 Subject Disposition**

Separately for Period 1 and Period 2, the number and percentage of subjects who are randomized, received at least one dose of study drug, prematurely discontinued study drug, prematurely discontinued study participation, and completed will be summarized by treatment group and overall. Reasons for premature discontinuation of study drug and study participation will be summarized separately for all randomized subjects by treatment group and overall, with frequencies and percentages by reason for discontinuation.

#### **8.1.2.3 Study Drug Exposure**

Exposure to study drug will be summarized for the Safety Analysis Set for Period 1 alone as well as for Period 1 and Period 2 combined. The exposure to study drug (days) will be summarized with the mean, standard deviation, median, and range for each treatment group.

Study drug compliance will be summarized for each treatment group. The compliance is defined as the number of tablets taken (i.e., the difference between the number of tablets dispensed and the number of tablets returned) during the subject's participation in Period 1 divided by the number of tablets a subject is supposed to take each day times the length of time that the subject was in the Treatment Phase.

